Jiao Tong University School of Medicine

Clinical Research Protocol

Project Name: Evaluation of the one-piece zirconia abutments and two-piece zirconia abutments with titanium bases for single implant crowns in esthetic region: a randomized split-mouth clinical trial with 1-year follow-up

Version Number: V 2.0

Version Date: 2020/12/10

Project Manager: [name]

Start and End Dates: 2020/12 – 2022/12

PROTOCOL TITLE:

Evaluation of the one-piece zirconia abutments and two-piece zirconia abutments with titanium bases for single implant crowns in esthetic region: a randomized split-mouth clinical trial with 1-year follow-up

Abstract

Objective: To evaluate the clinical, radiological and immunological outcomes of the one-piece zirconia abutments (OPZAs) and two-piece zirconia abutments (TPZAs) with friction-fitted titanium bases in single implant crowns in aesthetic region.

Materials and methods: The study is a single center, split-mouth and randomized controlled clinical trial. Eligible patients will be randomly assigned into two groups: OPZAs group (OG) and TPZAs group (TG). Survival rates, mechanical complication rates, bleeding on probing (BOP%), probing depth (PD), modified plaque index (mPI), marginal bone loss (MBL), concentrations of pro-inflammatory cytokines (TNF- α , IL-6) in peri-implant crevicular fluid (PICF), and pink esthetics score/white esthetics score (PES/ WES) will be evaluated.

Discussion: Results of the present study will help to evaluate the clinical, radiological and immunological outcomes of OPZAs and TPZAs with friction-fitted titanium bases in single implant crowns in aesthetic region and provide evidence for the effects of two types abutments on the health of peri-implant soft and hard tissue.

Keywords: zirconia abutment, one-piece, two-piece, peri-implant crvicular fluid, inflammatory factors, peri-implant diseases

1. Background

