2. METHOD/DESIGN

Overview

The present study is designed as a prospective, single-center, split-mouth, randomized controlled clinical trial. The investigators plan to recruit several adult patients who have two missing teeth in the maxillary anterior region and plan to be restored with two single implant crowns. The clinical component of the study will be initiated in Feb. 2019 at the Department of Oral and Maxillo-facial Implantology, Shanghai Ninth People's Hospital, Shanghai Jiao Tong University, China.

All patients received oral hygiene instruction and periodontal treatment before implant surgery.

The investigators will record the age, gender, physical health of all participants and they will meet the following inclusion criteria. Peri-apical radiographs with paralleling technique will be performed on the day of final restorations delivery. Clinical radiological and immunological re-evaluations will be performed at 1 year after the final crowns delivery.

Inclusion criteria

1) age \geq 18; 2) patients with two missing teeth in esthetic region and plan to be restored with two single implant crowns; 3) adjacent to natural teeth; 4) absence of oral mucosal disease and oral infection; 5) implants with conical connection (Nobel Active, Nobel Biocare® or NobelReplace Conical Connection, Nobel Biocare®); 6) patients with the willingness to participate in the present study.

Exclusion criteria

1)Heavy smokers (>10 cigarettes/day); 2) uncontrolled periodontitis (Full mouth plaque score $>20\%$, full mouth bleeding score $>25\%$, residual pocket depth $>5\text{mm}$); 3) with systematic diseases that may affect implant therapy, such as uncontrolled diabetes mellitus (Fasting blood-glucose $>7.2\text{mmol/L}$, Glycosylated hemoglobin $>7\%$), current intake of bisphosphonates (treatment for malignancy), pregnant(or plan to get pregnant), with history of radiation therapy in head and neck region.

Recruitment

Patients who have two missing teeth in the maxillary anterior region and plan to be restored

with two single implant crowns will be recruited at the Department of Oral and Maxillo-facial Implantology, Shanghai Ninth People's Hospital, Shanghai Jiao Tong University, China. Eligible patients will receive the study information and informed consent, and any patients who do not sign the consent will not be included in the study.

Allocation and blinding

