Eligible patients have two missing teeth, and they will be randomly assigned into two groups: OPZAs group (OG): restored with the OPZAs; TPZAs group (TG): restored with the TPZAs with friction-fitted titanium bases. The study is an open-label trial without blinding.

Outcomes

All the included patients will be recalled for clinical, radiological and immunological re-evaluations 1-year after the final crowns delivery. Survival rates, mechanical complication rates, bleeding on probing (BOP%), probing depth (PD), modified plaque index (mPI), marginal bone loss (MBL), concentrations of pro-inflammatory cytokines (TNF- α , IL-6) in peri-implant crevicular fluid (PICF), and pink esthetics score/white esthetics score (PES/ WES) will be recorded.

Survival rates.²⁵ The survival rate was defined as the percentage of success implants and remained crowns which never been replaced.

Mechanical complications rates. Veneer chipping, abutments or implants fracture, screw loosening or fracture and other mechanical complications will be recorded during the 1-year

follow-up.

Peri-implant conditions. The indicators of peri-implant conditions included bleeding on probing% (BOP%), pocket probing depth (PD) and modified plaque index (mPI).

Marginal bone loss (MBL).²⁶ Peri-apical radiographs with paralleling technique will be performed on the day of final restorations delivery and 1 year later. The implant length is used as calibration reference. The distance between restoration margin and the most coronal level of implant-bone contact will be recorded. The final result calculate as the mean value of mesial and distal sites. The alteration of the distance between baseline and 1-year follow-up is defined as the MBL.

Pro-inflammatory cytokines in peri-implant crevicular fluid (PICF). The investigators will collect the patients' PICF with the paper strip (PerioPaper Strips; Oraflow Inc., Smithtown, NY, USA) at 1-year follow-up to access differences in pro-inflammatory cytokines (IL-6 and TNF- α) between two groups. Enzyme-linked immunosorbent assay (ELISA) will be used to analyzed PICF and evaluated the concentrations of cytokines. The PICF collection method and cytokines determination referred to Christopher A. Barwacz et al (Figure 2).¹⁸

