PES/WES.^{27,28} In this study, pink aesthetic score (PES) and white esthetic score (WES) will be applied for the objective esthetic assessment of the final restoration. The investigators will take patients' intraoral photos by the camera (D70, Nikon, Tokyo, Japan) at 1 year follow up. The aesthetic effect will be assessed by two specific dentists independently. They will asked to give scores for variables of PES (Mesial papilla, distal papilla, level of soft-tissue margin, soft-tissue contour, alveolar process and soft-tissue color and texture) and WES (Tooth form, tooth volume/outline, color, surface texture and transparency) with the 0-1-2 scoring system. Final

PES/WES is the sum of the two.

The primary outcome variable is presupposed to be the success rates. And the null hypothesis is that there is no significant difference regarding mechanical complication rates between two groups.

Statistical analysis

All statistical analyses will be performed using SAS software, version 9.4 (SAS Institute). Normal tests will be performed to know the normality of continuous data before appropriate ways of statistical description and analysis were chosen. Means, standard deviations (SD) and student's t test will be used for data in accordance with normal distribution. Medians, inter quartile range (IQR) and Wilcoxon Rank Sum test will be used for non-normally distributed data. Qualitative data will be described and analyzed by percentage and Chi-square Test. A two-sided *P* value of less than 0.05 will be considered to indicate statistical significance.

Missing data

Sample size calculation was performed accounting for possible loss to follow-up. Moreover, the investigators will account for the data not missing at random due to unbalanced loss to follow-up by handling drop-outs as nonsuccess using the intention-to-treat principle.

Ethical considerations

Ethical approval

All eligible patients will receive study information and informed consent, and any patients who do not sign the consent will not be included in the study.

Withdraw

All patients in this study will be informed that they have the right to withdraw at any time during the study, regardless of whether they withdraw or not, the treatment required by the patients will be accepted.

4. Discussion

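### Scoring drop-outs as nonsuccess because of unbalanced loss does not fit whole-patient loss in a split-mouth trial, and the assumption is never varied

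*Combined protocol and SAP*

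**What the plan says.** All references are to the Combined protocol and SAP.

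- **Design.** The Abstract states: "The study is a single center, split-mouth and randomized controlled clinical trial". The Overview in the Method/Design section recruits patients with "two missing teeth in the maxillary anterior region and plan to be restored with two single implant crowns". A split-mouth trial therefore has one site per arm in each patient. Allocation and blinding, however, reads as if patients were assigned: "Eligible patients have two missing teeth, and they will be randomly assigned into two groups".
- **Follow-up.** Recall is by patient: "All the included patients will be recalled for clinical, radiological and immunological re-evaluations 1-year after the final crowns delivery". So is withdrawal: "All patients in this study will be informed that they have the right to withdraw at any time during the study".
- **Recording of complications.** Outcomes says: "Veneer chipping, abutments or implants fracture, screw loosening or fracture and other mechanical complications will be recorded during the 1-year" follow-up. An event can therefore be on file before a patient is lost.
- **Missing-data rule.** The plan will allow for "data not missing at random due to unbalanced loss to follow-up by handling drop-outs as nonsuccess using the intention-to-treat principle". It does not say whether a drop-out is a patient or a site, or what becomes of an event recorded before loss. No second assumption or sensitivity analysis appears anywhere.
- **Test.** Statistical analysis sends qualitative data to a chi-square test, two-sided at 0.05.
- **Primary outcome.** Background and the Objectives and Hypothesis section point to mechanical complication rates. The last paragraph of Outcomes names success rates, which are not defined.

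**The concern.** The rule is justified by loss that differs between arms. In a within-patient comparison, losing a patient cannot produce that. Only losing one site of a pair can.

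Applied to a patient lost whole, with nonsuccess read as failure on the primary outcome, the rule sets both sites to failed. The reported failure rates then partly measure attendance. The unpaired chi-square sees equal failures added to both arms and loses evidence. If one site already had a complication on record, its partner is failed as well, so a pair that favoured one abutment becomes a tie. The rule is also one fixed not-missing-at-random assumption, and the reader would not learn how far the answer depends on it.

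**Working it through.** **Inputs.** From the documents: two sites per patient, one per arm; the drop-out rule; an unpaired chi-square; two-sided 0.05. Missing data says that the sample size allowed for loss but gives no figure, so there is nothing to reproduce. Every sample size, event rate and loss below is an assumption. Failure means failure on whichever primary outcome applies.

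**1. Balance.** If m patients are lost whole, each arm loses m sites, and the difference is m − m = 0. Imbalance needs single-site loss.

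**2. Absolute rates and difference.** Let d be the share of patients lost whole and p the failure rate among completers. The rule reports p(1−d)+d in each arm. The difference becomes (1−d) times the completers' difference, because every lost pair contributes zero. If no lost patient had a recorded event, the true difference could lie anywhere in (1−d) × completers' difference ± d. Assume completer rates of 10% (one-piece) and 2% (two-piece), a difference of 8.0 points:

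| Loss d | One-piece, rule | Two-piece, rule | Difference, rule | Possible range |
|---|---|---|---|---|
| 5% | 14.5% | 6.9% | 7.6 | 2.6 to 12.6 |
| 10% | 19.0% | 11.8% | 7.2 | −2.8 to 17.2 |
| 20% | 28.0% | 21.6% | 6.4 | −13.6 to 26.4 |

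At 10% loss, for example, 0.10 × 0.9 + 0.10 = 0.190 and 0.02 × 0.9 + 0.10 = 0.118. Drop-outs then make up 0.10/0.190 = 53% of reported one-piece failures and 0.10/0.118 = 85% of two-piece failures.

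**3. No event recorded before loss.** Assume 30 patients and 3 lost. Among 27 completers, 6 pairs fail on the one-piece site only, none on the two-piece site only, and 1 on both. Chi-square is Pearson without correction. Exact McNemar for 6 v 0 is 2 × 0.5^6 = 0.031.

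| Handling | One-piece v two-piece | Difference | Chi-square p | McNemar p |
|---|---|---|---|---|
| Completers | 7/27 v 1/27 | 22.2 | 0.022 | 0.031 |
| Plan's rule | 10/30 v 4/30 | 20.0 | 0.067 | 0.031 |
| As recorded | 7/30 v 1/30 | 20.0 | 0.023 | 0.031 |
| Lost fail one-piece only | 10/30 v 1/30 | 30.0 | 0.003 | 0.004 |
| Lost fail two-piece only | 7/30 v 4/30 | 10.0 | 0.32 | 0.51 |

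The rule and status as recorded give the same difference. The rule moves the unpaired test across 0.05, while the paired test ignores the added concordant pairs.

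**4. One event recorded before loss.** Assume 40 patients and 4 lost, one of them after a one-piece complication. Completers have 5 v 0 failures of 36.

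| Handling | One-piece v two-piece | Difference | Discordant pairs | McNemar p |
|---|---|---|---|---|
| As recorded | 6/40 v 0/40 | 15.0 | 6 v 0 | 0.031 |
| Plan's rule, both sites failed | 9/40 v 4/40 | 12.5 | 5 v 0 | 0.063 |
| Rule, but partner of a recorded event not failed | 9/40 v 3/40 | 15.0 | 6 v 0 | 0.031 |
| Both sites assessed at 1 year | 5/36 v 0/36 | 13.9 | 5 v 0 | 0.063 |
| Lost fail one-piece only | 9/40 v 0/40 | 22.5 | 9 v 0 | 0.004 |
| Lost fail two-piece, recorded event kept | 6/40 v 4/40 | 5.0 | 5 v 3 | 0.73 |

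Under the plan's rule the planned chi-square gives p=0.13. The recorded complication is still among the nine one-piece failures. What has gone is the contrast with its partner. In row three the one-piece count is 5 + 1 + 3 = 9 and the two-piece count is 0 + 3 = 3.

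**The case against.** The strongest reply is that failure imputation keeps every randomised patient, agrees with the stated intention-to-treat principle, and is a deliberate choice. Moreover, the obvious alternative, status as recorded, also sets an event-free lost patient's difference to zero, and does so optimistically: a fracture after loss counts as no event. That stands. Choosing between the two as primary is a trade-off, so the case does not require the sponsor's rule to be replaced.

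Three further limits stand:

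- A reader might infer that the rule erases recorded complications. It does not: the affected site still counts as nonsuccess. Only the between-site contrast can be lost, and only if drop-out means the whole patient and nonsuccess means failure on that outcome. The document settles neither.
- A reader might infer that unbalanced loss is impossible here. Single-site loss can be unbalanced, and the Missing data text does not exclude that meaning.
- The wide ranges follow from any missing binary data and need every lost patient to fail in one arm only. The second example places one event so that p moves from 0.031 to 0.063, and the both-sites-assessed analysis gives 0.063 too.

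Part of the harm comes from the unpaired test rather than the rule. That does not remove the point, because the plan pairs the two: applied as written to event-free lost patients, they take the first example from 0.022 to 0.067. Nor does it answer the lack of any second assumption.

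**Conclusion.** The concern holds in a limited form. The stated reason does not fit patients lost whole. On the reading that a drop-out is a patient and nonsuccess is a failure on the primary outcome, the rule raises both absolute rates with non-attendance (10% v 2% becomes 19.0% v 11.8% at 10% loss), weakens the planned chi-square, and can turn a recorded one-sided complication into a tie. Shrinkage of the difference is modest at low loss: a factor of 0.90 at 10%. The larger faults are the inflated absolute rates, the mismatch with the unpaired test, and a single untested assumption.

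These sizes rest on assumed sample sizes, event rates and loss. The documents do not support a claim that the trial's result would be reversed, or that the rule is wrong as one analysis among several. This is worth changing before analysis. Confidence is medium because the text leaves the key terms undefined.

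**What to change.** 1. Analyse the binary primary outcome as paired: exact McNemar with a paired risk difference. Added concordant pairs then do not dilute the test.
2. Define drop-out separately for patients and for sites, and confine the unbalanced-loss reason to site-level loss. Reconcile the Abstract and Allocation wording, which reads as assigning patients, with the split-mouth design. Keep each site's status recorded before loss, so that a partner site is not failed in a patient who already has a recorded event.
3. The drop-out-as-nonsuccess rule may stay as the primary or a supporting analysis. Report beside it (a) status as recorded up to loss, (b) patients with both sites assessed at 1 year, and (c) discordant best and worst cases, with lost patients' sites failing in one arm only and then in the other, recorded events kept.
4. State which primary outcome the rule serves, mechanical complications or success, and define nonsuccess to match.

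**Cost.** Revised wording and a few small tables, with no new data. The discordant range may be wide in a small trial. Status as recorded may understate absolute rates, and it gives the same difference as the sponsor's rule when no lost patient had a recorded event.
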